## **9.6 Vital Signs**

Vital signs (blood pressure, respiratory rate, heart rate, oxygen saturation and temperature) will be summarized using descriptive statistics at baseline and at each post-baseline time point. Changes from baseline will also be summarized.

All vital signs data will be provided in listings.

## **9.7 Physical Examination**

Physical examination results, including weight, will be listed. This listing will include data from each full physical exam (Screening and Follow-up/End of Treatment visits) and also assessments for physical symptoms/toxicities (recorded at each visit during the treatment period).

## 9.8 Electrocardiogram

Overall interpretation results for ECG will be summarized using shift tables (Normal, Abnormal NCS, Abnormal CS) comparing baseline to follow-up. Descriptive statistics at baseline and at each post-baseline time point as well as changes from baseline will be summarized for each ECG parameter.

All ECG results will be listed.

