3. Pre-treatment bladder tumor tissue sample will be obtained during in-office cystoscopy by cold cup biopsy within 4 weeks of TURBT. Post-treatment bladder tissue sample will be obtained at surgical resection (TURBT) on Day 5.
4. Hematology will include measurement of hemoglobin, hematocrit, platelets, RBC, reticulocytes, and WBC with differential.
5. Clinical chemistry will include measurement of potassium, sodium, chloride, glucose, BUN, creatinine, creatinine clearance, ALT, AST, GGT, alkaline phosphatase; indirect bilirubin, direct bilirubin, total bilirubin, total protein, albumin, calcium, bicarbonate, magnesium, phosphate, lipase, and amylase.
6. Urinalysis will include color, turbidity, pH, specific gravity, glucose, ketones, nitrites, bilirubin, urobilirubin, protein, RBCs, WBCs, epithelial cells, casts, crystals, and bacteria, and eGFR at Screening only.
7. A full physical examination will be conducted at Screening and at Visit 7/Follow-up. At each other study visit, patients will be assessed for continued dosing and any possible physical symptoms/toxicities and a physical examination may be performed, if indicated. Body weight should be measured at each study visit. Height should be measured at Screening.
8. Vital signs will be measured before any blood draws scheduled for the same time point. Vital signs will include blood pressure, respiratory rate, pulse, oxygen saturation, and temperature.
9. At Screening, 12-lead ECGs will be performed in triplicate, with each measurement separated by 2 minutes. The average of the 3 screening ECGs will be used to calculate QTc interval to determine study eligibility. Thereafter, single 12-lead ECGs will be performed for all patients prior to drug administration on Days 1 and 5 and at the Final Study visit.
10. All AEs and SAEs will be collected from the signing of the informed consent form through the time of TURBT. Starting at TURBT, only AEs related to CPX-POM treatment should be recorded; AEs related to the TURBT will not need to be recorded.
11. All concomitant medications will be recorded from the time of Screening up to the time of TURBT. Starting at TURBT, only medications associated with an AE related to CPX-POM treatment need to be recorded; routine medications and medications associated with the TURBT procedure do not need to be recorded.

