## 7. STUDY POPULATION

### 7.1 Patient Disposition

Patient disposition information will be summarized for all patients by treatment group (only 900 mg/m^2 CPX-POM). Summaries will include: the number of patients screened, the number of patients in each analysis set, the number of patients completing the study, the number of patients completing 5 days of dosing with CPX-POM and who undergo TURBT from which tissue, blood, and urine samples were collected, the number of patients who completed the Day 35 Follow-up Visit, the number of patients who died and the primary cause of death, the number of patients who had an autopsy, and the primary reason for discontinuation.

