### **9.1 Baseline Values**

Baseline is be defined as the measurement taken at baseline safety assessment Visit #2 (Study Day 1). If that measurement is not available, baseline is defined as the last non-missing measurement recorded prior to CPX-POM administration.

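### On its natural reading, the SAP's ECG shift table runs from baseline to Day 35 only and leaves out the Day 5 pre-dose interpretation (minor)

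*SAP*

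**What the plan says.** SAP 9.8 plans three ECG outputs.

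- Interpretation: "Overall interpretation results for ECG will be summarized using shift tables (Normal, Abnormal NCS, Abnormal CS) comparing baseline to follow-up".
- Numeric parameters: "Descriptive statistics at baseline and at each post-baseline time point as well as changes from baseline will be summarized for each ECG parameter".
- Listing: "All ECG results will be listed".

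The ECG schedule is in Protocol 1.3, Table 1, footnote 9. After the triplicate at Screening, "single 12-lead ECGs will be performed for all patients prior to drug administration on Days 1 and 5 and at the Final Study visit". SAP 9.1 takes the Day 1 measurement as baseline, falling back on the last value before dosing. Two scheduled post-baseline ECGs remain: Day 5 before the fifth infusion, and the final visit.

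SAP 9.8 does not say which visit *follow-up* means. SAP 7.1 counts "the number of patients who completed the Day 35 Follow-up Visit". SAP 9.7 uses the term for a named visit, distinct from the treatment-period visits, and Protocol Table 1 puts it at the head of the Day 35 column.

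**The concern.** The shift table is the only planned summary of the investigator's judgement that an ECG is normal, abnormal but not clinically significant, or abnormal and clinically significant. If it pairs baseline with Day 35 alone, it compares an ECG taken before any drug with one taken about 30 days after the last dose. The scheduled ECG that falls within the dosing period then contributes nothing to it.

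ECGs are among the criteria for the primary safety and tolerability objective (Protocol 1.1, Criteria for Evaluation). A reader who turns to the table for a count of clinically relevant ECG change during treatment would not find it there, and could take a row of unchanged patients as evidence about the dosing period. The Day 35 ECG also comes after the resection, which makes a shift at that visit harder to attribute to drug.

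**Working it through.** There is no stated figure to reproduce. The sample size of 12 has no calculation behind it (SAP 4), and the point concerns how a table is specified.

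**Step 1: what *follow-up* covers.** Two adjacent sentences in SAP 9.8 use different terms. The interpretation goes from baseline to *follow-up*; the numeric parameters are given as "Descriptive statistics at baseline and at each post-baseline time point". Had the first sentence meant every later ECG, the wording of the second was available. Together with SAP 7.1, SAP 9.7 and Protocol Table 1, this makes Day 35 the natural reading. It is an inference, because the word is in lower case and carries no visit label.

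**Step 2: which ECGs enter which output, on that reading.**

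| Scheduled ECG | Interpretation shift table | Numeric summaries | Listing |
|---|---|---|---|
| Day 1, pre-dose (baseline) | yes | yes | yes |
| Day 5, pre-dose | no | yes | yes |
| Day 35 | yes | yes | yes |

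The shift table uses one of the two scheduled post-baseline ECGs. Up to 12 of 12 Day 5 interpretations stay out of it.

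**Step 3: effect on the count.** Suppose k of 12 patients are normal at baseline, abnormal on Day 5 and normal on Day 35. For these patients the baseline-to-Day 35 table shows 0/12 shifts. A baseline-to-Day 5 or baseline-to-worst table shows k/12:

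- k = 1: 1/12 = 8.3%
- k = 2: 2/12 = 16.7%
- k = 3: 3/12 = 25.0%

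The documents give no rate for such transient findings. For an assumed per-patient rate p, the chance of at least one among 12 is 1 − (1 − p)^12:

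- p = 5%: 1 − 0.95^12 = 46%
- p = 10%: 1 − 0.90^12 = 72%
- p = 20%: 1 − 0.80^12 = 93%

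These rates are illustrations, not expectations.

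**Step 4: what the Day 5 ECG can show.** Protocol 2.1 gives a CPX half-life of typically 2 to 6 hours. The Day 5 ECG precedes the fifth infusion, so it falls about 24 hours after the fourth.

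- Half-lives elapsed: 24/6 = 4 to 24/2 = 12.
- Fraction of CPX left: 0.5^4 = 6.25% to 0.5^12 = 0.02%.
- For Day 35: 30 × 24 = 720 hours, so 720/6 = 120 to 720/2 = 360 half-lives after the last dose.

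Day 5 is therefore a near-trough ECG after four doses. It can reveal an effect that lasts about a day, not one at peak concentration. It is still much closer to exposure than Day 35.

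**Step 5: the SAP's own comparator.** For laboratory data, SAP 9.5 counts grade increases over the post-baseline period through the last dose. That categorical summary covers the treatment period; the ECG one, on the natural reading, compares baseline only with a visit after it. The SAP gives no reason for the difference.

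**The case against.** The strongest reply is that little is hidden.

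- **Listing.** All ECG results are listed. With 12 patients and two scheduled post-baseline ECGs each, that is about 24 post-baseline records, in which a normal–abnormal–normal course can be read patient by patient. This stands. A reader might infer that the Day 5 interpretations are dropped from the report; the documents do not support that.
- **Numeric summaries.** Day 5 parameters are summarized with change from baseline, and SAP 5 requires minimum and maximum as well as mean and median. An extreme value in one patient would be visible. This also stands, although these statistics do not carry the investigator's category.
- **Adverse events.** The general definition in Protocol 8.1.1.1 is wide enough for a clinically significant ECG finding. The Day 5 ECG precedes TURBT, when all adverse events are still collected, so a recorded finding would enter the SAP 9.4 tables. This stands in part. Protocol 8.1.3.7 tells sites to record clinically significant laboratory abnormalities as adverse events, but the ECG section (8.1.3.6) has no matching instruction.
- **Wording.** Lower-case *follow-up* could mean any post-baseline ECG, and the SAP speaks of shift tables in the plural. A reader might take the SAP to exclude Day 5 expressly; it does not. The ambiguity itself needs resolving, since two programmers could build different tables from the sentence.
- **Prior data.** Protocol 2.1 reports no QTc prolongation or other ECG abnormality at doses up to 1200 mg/m². That lowers the expected yield but does not bear on whether the table covers the right visits.

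**Conclusion.** The point holds as a minor one. On the natural reading of SAP 9.8, the interpretation shift table leaves out the only scheduled ECG after dosing starts and before treatment ends, so an abnormality seen on Day 5 and resolved by Day 35 is tabulated as no shift. The size is one table cell per affected patient: 0/12 instead of 1/12 (8.3%) for a single case.

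This rests on two assumptions: that *follow-up* means the Day 35 visit, which the SAP implies but does not state, and that such a transient finding occurs, for which the documents give no rate.

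A reader might go further and conclude that the plan conceals abnormalities at drug exposure. The documents do not support that: the Day 5 ECG is near trough, the results are reported elsewhere, the analysis is descriptive (SAP 9), and no decision rule uses this table.

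**What to change.** Reword the first sentence of SAP 9.8 so that it names the visits, for example: *shift tables comparing baseline to each post-baseline ECG (Day 5 and Day 35/early termination) and to the worst post-baseline interpretation, including unscheduled ECGs*.

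The Day 5 columns close the gap. The worst-post-baseline columns add the unscheduled ECGs and give one count per patient. The cost is one SAP sentence and a few extra table columns, all from data already collected, with no new assessment and no change to patient management. The results should be described as near-trough findings so that the added columns are not read as evidence about peak exposure.

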## 9.9 Other Safety Measurements

The following safety measurements collected will also be provided in listings:

- Echocardiogram
- Chest X-Ray or CT Scan
- Pregnancy Test Results

## 9.10 Study Procedures

The details of the following procedures will be provided in listings:

- Cytoscopy/Biopsy Procedures
- Transurethral Resection of Bladder Tumor (TURBT)

## 10. PHARMACOKINETIC ANALYSES

Tissue, plasma, and urine concentrations of CPX-POM and its metabolites will be determined by GLP-validated liquid chromatography with tandem mass spectrometry LC-MS/MS assays and results will be presented in by-patient listings.

Bladder tumor tissue-to-plasma and tissue-to-urine CPX concentration ratios will be calculated for each patient and listed.

Urine  $\beta$ -glucuronidase activity, expressed as units of activity per milliliter of urine as well as units of activity per milligram of urine creatinine, will be measured for each patient and listed.

These results will be reported separately.

## 11. PHARMACODYNAMIC ANALYSES

Bladder tumor tissues will be analyzed using single cell sequencing to elucidate mechanisms of CPX-POM action. To determine the change in bladder tumor tissue cell proliferation, Notch and Wnt cell signaling pathways, as well as bladder tumor tissue CD8+ TIL, immunohistochemistry will be performed on paraffin-embedded slides.

These results will be reported separately.

## 12. REFERENCES

## 13. SOFTWARE

SAS Software Version 9.4. SAS Institute Inc., Cary, NC, USA.

## 14. SAP REVISIONS

Revision Date (dd month, yyyy)	Section	Summary of Revision	Reason for Revision
